## Synopsis

**Study Title:** Canadian Pradaxa Acute Stroke Safety Study (CPASS)

**Protocol Number:** CSC2012-01

**Development Phase:** Phase IV Registry

**Indication:** Minor Stroke (NIHSS Score  $\leq 3$ ) and Transient Ischemic Attack Patients with a known history of or demonstrated atrial fibrillation (paroxysmal or persistent), who can be treated with dabigatran following stroke.

**Study Drugs:  
(Including test,  
comparator, dosage  
form, dosing regimen  
and route)** Dabigatran Etxilate  
Dose: 150 mg PO BID OR 110 mg PO BID (dose determined by patient age and renal function)  
Route: PO  
  
Comparator : None (open label, single arm trial)

**No. Subjects:** 500

**No. Centres:** 15 centres within Canada

**Study Duration:** 2 years. Patients will participate in the trial for 1 month.

**Objectives of the Study:** The primary aim of the CPASS registry is to demonstrate the safety of early anticoagulation with dabigatran following cardioembolic stroke. Safety will be established by demonstrating low rates of hemorrhage in this setting.

**Study Endpoints:  
(Primary and  
Secondary)** *Primary Outcome*  
Symptomatic Hemorrhagic Transformation Rate (PH2) associated with clinical deterioration, defined as worsening of NIHSS score of 4 or more points within 30 days of initiating dabigatran therapy.

*Secondary Outcomes*  
Any parenchymal haemorrhage (PH1 or PH2) on follow-up CT scan at 7 $\pm$ 2 days post-enrolment

Symptomatic hemorrhagic transformation rate (defined as above) in patients treated with warfarin prior to the index stroke/TIA.

Recurrent TIA/Ischemic Stroke within 30 days of enrolment  
 Systemic hemorrhagic complication rate within 30 days of enrolment

**Study Design:**

Multicentre, prospective, open-label, single arm phase IV study.

**Eligibility Criteria (Inclusion and Exclusion)****Inclusion criteria**

1. All patients will be  $\geq 18$  years of age.
2. Minor ischemic stroke, defined as NIHSS score  $\leq 3$ . Transient Ischemic Attack (TIA), defined as acute focal neurological deficits, with complete resolution of symptoms within 24 h of onset. In cases where onset time cannot be established, it will be considered to be the time when the patient was last known to be well.
3. Atrial Fibrillation (AF, paroxysmal or persistent). AF must be confirmed with ECG/Holter monitor, or by history. All patients prescribed dabigatran according to the Canadian product label by the treating physician following their stroke/TIA. The decision to treat with dabigatran and the timing of the first dose will be determined by the attending physician, independent of the registry. All patients will have a CT scan or MRI, with findings consistent with an ischemic etiology of symptoms.
4. Ability to obtain informed consent obtained from patient or legally authorized representative.

**Exclusion criteria**

1. Acute or chronic renal failure, defined as eGFR  $<30$  ml/min (Cockcroft Gault formula).
2. Known hypersensitivity to dabigatran or any other contraindication to dabigatran therapy, as per Canadian label information.
3. Prior treatment with dabigatran or any other novel oral anticoagulant (including all Factor Xa antagonists). Treatment with warfarin prior to the stroke/TIA is acceptable, but enrolment cannot begin until the INR is  $\leq 1.5$ .
4. Prior symptomatic ischemic stroke (TIA is not an exclusion criterion)
5. Any significant ongoing systemic bleeding risk, i.e.

active GI/GU bleeding or recent major surgery.

6. Clinically significant recent past history or clinical presentation of ICH, subarachnoid haemorrhage (SAH), arterio-venous (AV) malformation, aneurysm, or cerebral neoplasm. At the discretion of each Investigator.
7. Hereditary or acquired hemorrhagic diathesis.
8. Anticipated inability to comply with follow up.
9. Any condition that, in the judgment of the investigator could impose hazards to the patient if study therapy is initiated or affect the participation of the patient in the study.

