morbidities, particularly hypertension, diabetes, hypercholesterolemia and ischemic heart disease, CHADS-Vasc, HAS-BLED, history of gastrointestinal or other hemorrhage will all be recorded (**Appendix 1**).

**3.3.1 Patients.** Male and female patients with acute TIA or ischemic stroke will be recruited from the Emergency Departments and stroke units at CSC investigator sites. All patients will have documented evidence of atrial fibrillation (permanent or paroxysmal). Informed consent will be obtained from patients or surrogate decision makers prior to enrolment in all cases.

**3.3.2 Inclusion Criteria.** All patients will be 18 years or older. Eligible patients will have ischemic stroke (NIHSS score  $\leq 3$ ) or TIA (complete resolution of focal neurological deficits within 24 hours) and atrial fibrillation (paroxysmal or persistent). The decision to treat with dabigatran and the timing of the first dose will be determined by the attending physician, independent of the registry. In cases where stroke onset time cannot be established, it will be considered to be the time when the patient was last known to be well. All patients will have a CT scan or MRI, with findings consistent with an ischemic etiology of symptoms. Patients taking warfarin *prior to* the stroke/TIA will be eligible, but INR must be  $\leq 1.5$  prior to initiation of dabigatran.

**3.3.3 Exclusion Criteria.** Patients in whom dabigatran is contraindicated according to the Canadian product monograph will not be eligible, i.e. severe renal failure or significant ongoing bleeding risk, will not be eligible. These specific contraindications in the Canadian product monograph at the time are:

- Severe renal impairment (CrCl  $< 30$  mL/min)
- Hemorrhagic manifestations, bleeding diathesis, or patients with spontaneous or pharmacological impairment of hemostasis
- Lesions at risk of clinically significant bleeding, e.g. extensive cerebral infarction (hemorrhagic or ischemic) within the last 6 months, active peptic ulcer disease with recent bleeding
- Concomitant treatment with strong P-glycoprotein (P-gp) inhibitors, i.e. oral ketoconazole
- Known hypersensitivity to dabigatran or dabigatran etexilate or to any ingredient in the formulation or component of the container

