- Concomitant treatment of dabigatran etexilate with any other anticoagulant, including unfractionated heparin (UFH), except at doses used to maintain a patent central venous or arterial catheter, low molecular heparins (LMWH), such as enoxaparin and dalteparin, heparin derivatives, such as fondaparinux, anti-thrombin agents, such as bivalirudin, and oral anticoagulants, such as warfarin, rivaroxaban, apixaban, except under circumstances of switching therapy to or from dabigatran
- Presence of prosthetic heart valve(s) requiring anticoagulation due to valvular status itself

Patients with a history of symptomatic ischemic stroke prior to the index event will not be eligible. All patients taking dabigatran or any other novel oral anticoagulant (including all Factor Xa antagonists) prior to the stroke will be ineligible. Individuals on warfarin at the time of the incident event are eligible, provided the INR is  $\leq 1.5$  prior to initiation of dabigatran.

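### The INR limit for prior-warfarin patients is tied to enrolment in the synopsis but to the first dabigatran dose in section 3.3, and the timing strata ignore anticoagulants given between the event and dabigatran

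*Combined protocol and SAP*

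**What the plan says.** **INR limit.** Synopsis exclusion criterion 3: "Treatment with warfarin prior to the stroke/TIA is acceptable, but enrolment cannot begin until the INR is" 1.5 or below. Section 3.3.2: "Patients taking warfarin *prior to* the stroke/TIA will be eligible, but INR must be" 1.5 or below before dabigatran is started. Section 3.3.3 repeats this: "Individuals on warfarin at the time of the incident event are eligible, provided the INR is" within that limit before the start of dabigatran.

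**Earlier dabigatran or other novel anticoagulant.** Synopsis exclusion criterion 3 opens with "Prior treatment with dabigatran or any other novel oral anticoagulant" and gives no date by which prior is judged. Section 3.3.3 excludes patients who were taking such a drug before the stroke.

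**Order of enrolment and first dose.** Synopsis inclusion criterion 3 says that "the timing of the first dose will be determined by the attending physician, independent of the registry". Section 3.3 keeps a log of all consented patients, treated or not, and follows only the treated ones.

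**Other anticoagulants.** Section 3.3.3 lists as a contraindication "Concomitant treatment of dabigatran etexilate with any other anticoagulant, including unfractionated heparin (UFH" and further agents, warfarin among them, "except under circumstances of switching therapy to or from dabigatran". It also lists "Hemorrhagic manifestations, bleeding diathesis, or patients with spontaneous or pharmacological impairment of hemostasis", with no laboratory cut-off. Section 7.1 expects no patient to take dabigatran together with another antithrombotic.

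**Timing.** Section 4.1 admits patients who start dabigatran up to 14 days from onset. Section 7.1 stratifies by days to the start of therapy (0-2, 3-7, more than 7). The secondary outcomes in section 5 and the synopsis paragraph on statistical analyses compare hemorrhagic transformation between starts within 7 days and later starts.

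**The concern.** Two separate matters arise.

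First, a safety-related entry rule is attached to two different events. Prior warfarin use is the primary stratification variable in section 7.1, and hemorrhagic transformation in that group is a named secondary outcome. If centres differ on which prior-warfarin patients may enter, the group behind that outcome is not defined in the same way across the registry.

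Second, the timing comparison is meant to describe early against later starts. A patient who received heparin or warfarin in the first days and moved to dabigatran in the second week is counted as a late start. A reader of the tables could not tell that patient from one who had no anticoagulant until then.

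**Working it through.** No figure in the plan is in dispute, so the check is a comparison of the texts.

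**Step 1: the INR anchor.** Take a prior-warfarin patient whose first dabigatran dose is given with an INR above 1.5, and whose INR later falls to 1.5 or below.

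- Sections 3.3.2 and 3.3.3: not eligible, because the limit was not met before the first dose.
- Synopsis, INR clause alone: satisfied once the INR has fallen.
- Synopsis, prior-dabigatran clause: the answer depends on the missing date. If prior means before enrolment, the patient is excluded and the two sections agree. If it means before the stroke, as in section 3.3.3, this clause does not exclude the patient and the two sections disagree.

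The INR conflict and the undated exclusion therefore have to be settled together.

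**Step 2: the opposite order.** Take a prior-warfarin patient with an INR above 1.5 at consent, which falls to the limit before the first dose. Section 3.3 admits the patient without further condition on the date of enrolment. The synopsis holds enrolment back until the INR has fallen. The date of enrolment then differs between the two rules even though the patient qualifies under both in the end.

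**Step 3: do enrolment and first dose coincide?** Nothing says so. The treating physician sets the time of the dose without reference to the registry, and the log of consented patients includes some who are never treated.

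**Step 4: anticoagulants after the event.** Both INR rules concern warfarin taken before the event. The concomitant-treatment contraindication covers overlap with dabigatran and exempts switching. Sequential use is left: for example, heparin from day 2, stopped or switched, and dabigatran from day 9. Day 9 lies inside the 14-day window, so the patient is admitted and falls in the stratum of more than 7 days.

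**Step 5: would the planned analysis or data show this?**

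- The sensitivity analysis in section 7.1 deals with stopping dabigatran or switching away from it, not with what preceded it.
- Appendices 2 and 3 have a treatment row for lysis and surgery, and none for interim anticoagulants.
- Section 6.1 records medications and a baseline coagulation profile, Appendix 1 has a medication list, and Appendix 5 asks about other drugs that influenced timing. The synopsis collects INR when ordered, within 20 days.
- None of these requires the last INR before the first dose or the dates of an interim anticoagulant.

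**The case against.** The strongest case against the first part is that this is loose wording and not two rules. The documents swap enrolment and initiation elsewhere: the synopsis counts 30 days for recurrent events from enrolment, section 5 from dabigatran initiation. Taken literally, the undated dabigatran exclusion already bars anyone dosed before enrolment. The log of consented patients suggests that enrolment comes first. The label contraindications, which synopsis exclusion criterion 2 brings in, may also catch a patient dosed with a raised INR. Much of this stands: on one natural reading the conflict over the patient in step 1 disappears. But it is one reading among several, and the impaired-hemostasis item gives no INR value that would settle it.

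Against the second part, concomitant heparin and warfarin are already excluded, and the stated question is when to start dabigatran, not when to start any anticoagulant. Both points stand. Redefining time as time to any first anticoagulant would answer a different question, and it is not suggested here. Section 7.2 calls the study hypothesis generating, and the expected 0.6% symptomatic rate in section 2.3 gives 0.006 × 500 = 3 events, so any further split produces sparse cells. That argues for a simple descriptive display. It does not argue for leaving interim anticoagulation unrecorded.

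**Conclusion.** Two limited points hold. The passages contradict each other on the event to which the INR limit attaches and on the date for the prior-dabigatran exclusion. They must be reconciled; no view is taken on which is right. The late-start stratum can also contain patients anticoagulated earlier, and the plan has no means of showing them. The first point has practical effect only if some patients are enrolled at a different time from their first dose, which the documents leave open.

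Three stronger conclusions might be inferred, and the documents do not support them.

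- *That the INR conflict mixes the primary stratum.* Section 7.1 defines that stratum by warfarin use before the event. The conflict can change who is eligible, but it moves nobody between strata.
- *That the effect on the timing comparison can be sized from the 1.7% heparin figure.* The documents give no frequency of interim anticoagulation. Section 1.1 uses 1.7% as an increase in transformation, while section 2.3 uses it as the symptomatic risk itself. The primary outcome window in section 5.1.2 opens when dabigatran starts, so bleeds on earlier heparin fall before it. Direction is open too, since patients who bled on an interim drug might never start dabigatran.
- *That the protocol itself shows bridging to be common.* The remark in section 1.1 about continued warfarin use concerns patients given warfarin instead of dabigatran, and section 3.3 does not follow them.

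**What to change.** 1. Reconcile synopsis exclusion criterion 3 with sections 3.3.2 and 3.3.3 so that the INR condition attaches to one named event and the exclusion for earlier dabigatran or other novel anticoagulants has one reference date. State how the time of enrolment relates to the first dose.
2. Record from existing records the last available INR before the first dabigatran dose, with its date, and any anticoagulant given between the event and that dose, with start and stop dates.
3. Keep time to dabigatran as the timing variable. Show the three timing strata, and the comparison of starts within 7 days against later starts, with and without patients who had interim anticoagulation.

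The cost is a wording amendment, two or three CRF fields that need no new procedure, and one extra split with smaller cells in a descriptive table.

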**Study Procedures:**

This is a phase IV registry study. No additional procedures are included in the study. Standard clinical data will be collected. This will include a physical examination and NIHSS score assessment at baseline.

In addition, all neuro-imaging will be collected. Standard imaging includes a non-contrast CT brain at baseline and 7±2 days post-treatment.

Repeat NIHSS score assessment at the time of the 7 day CT scan.

Repeat clinical and NIHSS score assessment 30 days post-enrolment will also be collected when performed as part of standard care.

**Safety  
Parameters/analysis:**

An independent DSMB will be sent blinded outcome data, including all cases with symptomatic or asymptomatic parenchymal haemorrhage. The DSMB will review adverse events after every 100 patients recruited.

**Imaging  
Parameters/Analysis**

All imaging data collected as part of standard care will be sent to the core imaging lab for analysis.

**Image Analysis.** Dicom CT data will be transferred to the Stroke Imaging Laboratory at the University of Alberta for post-processing and analysis. All image assessments will be performed using the Quantomo software package (Cybertrial Inc, Calgary, AB).

All cases of hemorrhagic transformation seen on day 7 scans will be graded using the ECASS (European Cooperative Acute Stroke Study) hemorrhage classification scheme:

1. PH2 - parenchymal hemorrhage as a blood clot in more than 30% of the infarcted area with substantial space-

- occupying effect.
2. PH1 - parenchymal hemorrhage as blood clots in 30% or less of the infarcted area with some slight space-occupying effect.
  3. HT2 - hemorrhagic transformation 2 - confluent petechiae within the infarcted area but no space-occupying effect.
  4. HT1 - hemorrhagic transformation 1 – small petechiae along the margins of the infarct.
  5. R - remote ICH, i.e. not topographically related to the infarct (most often in the contralateral hemisphere).

*A symptomatic ICH will be defined as PH2, associated with an NIHSS deterioration of  $\geq 4$  points.*

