## **5. Variables and Assessment.**

**5.1.1 Effectiveness.** This is a registry of the safety of early anticoagulation (see 5.2). A measure of the effect of early anticoagulation will be assessed; the rate of new ischemic stroke/TIA occurrence within the 30-day study period will be recorded. It is recognized that the event rate will be low and the study is neither designed, nor powered to demonstrate a decrease in early ischemic stroke rates.

**5.1.2 Primary Outcome (Safety).** The primary study outcome measure is the symptomatic hemorrhagic transformation rate (PH2 associated with clinical deterioration, defined as worsening of NIHSS score of 4 or more points, within 30 days of initiating dabigatran therapy).

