### **5.2.3 Assessment of safety laboratory parameters.**

**Imaging Data Collection.** No additional imaging will be required for study participants. Only standard clinical data will be collected. Acute baseline CT scans will be collected. Dicom files will be transferred to a central imaging database. All patients will have a follow-up non-contrast CT scan  $7\pm 2$  days after enrolment, in order to assess for early asymptomatic hemorrhagic transformation. In the event of any clinical deterioration, a repeat CT scan will be performed immediately. In addition, any supplemental brain imaging completed within the first 30 days after enrolment will be collected.

**Image Analysis.** Dicom CT data will be transferred to the Stroke Imaging Laboratory at the University of Alberta for post-processing and analysis. All image assessments will be performed using software developed specifically for CT brain image analysis (Quantomo software package, Cybertrial Inc, Calgary, AB). The extent of any objective acute and chronic ischemic changes on all CT scans will be

assessed using Alberta Stroke Program Early CT Scores (ASPECTS). It is expected baseline scans will not have evidence of acute ischemic changes, but this will be verified centrally. The extent of periventricular leukoariosis will also be measured using planimetric techniques and an intensity threshold algorithm included in the Quantomo software package.

All cases of hemorrhagic transformation seen on post-dabigatran treatment scans will be graded using the ECASS (European Cooperative Acute Stroke Study) hemorrhage classification scheme:

6. PH2 - parenchymal hemorrhage as a blood clot in more than 30% of the infarcted area with substantial space-occupying effect.
7. PH1 - parenchymal hemorrhage as blood clots in 30% or less of the infarcted area with some slight space-occupying effect.
8. HT2 - hemorrhagic transformation 2 - confluent petechiae within the infarcted area but no space-occupying effect.
9. HT1 - hemorrhagic transformation 1 – small petechiae along the margins of the infarct.
10. R - remote ICH, i.e. not topographically related to the infarct (most often in the contralateral hemisphere).

*A symptomatic ICH will be defined as PH2, associated with an NIHSS deterioration of  $\geq 4$  points.*

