## **6. Investigational Plan**

**6.1 Visit Schedule / Clinical Data Collection.** No additional procedures or assessments will be mandated for study participants. Standard clinical assessments and data will be collected. This will include baseline National Institutes of Health Stroke Scale NIHSS, Glasgow Coma Scale (GCS) and vital signs, which will be recorded in a case report form. Stroke risk factors, past medical history and medications, baseline complete blood count, coagulation profile and renal function tests will also be recorded. CHADS2 and CHADSVaSC scores will also be recorded. Clinical endpoints will be ischemic stroke or intracranial hemorrhage within 30 days of anticoagulant initiation. All cerebral ischemic and intracranial hemorrhagic endpoints will be centrally adjudicated from anonymized clinical records, with the intracranial hemorrhages classified as described above. A data collection form will be filled out for each subject at 30 days post-enrolment indicating clinical status and occurrence of outcome events.

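### The primary outcome needs a 4-point NIHSS worsening with PH2, but no NIHSS is specified at deterioration and no rule classifies a fatal or unscored PH2

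*Combined protocol and SAP*

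**What the plan says.** **Outcome.** Section 5.1.2 (Primary Outcome) asks for PH2 together with clinical deterioration, "defined as worsening of NIHSS score of 4 or more points, within 30 days of initiating dabigatran therapy". The Synopsis (Study Endpoints) agrees. Section 5.2.3 applies the same pairing to symptomatic ICH, and neither section offers an alternative for a patient who dies or has no score.

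**When NIHSS is named.** The Synopsis (Study Procedures) lists three occasions: baseline ("This will include a physical examination and NIHSS score assessment at baseline"), the day 7 CT, and day 30 on a conditional basis ("Repeat clinical and NIHSS score assessment 30 days post-enrolment will also be collected when performed as part of standard care").

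**At deterioration.** Section 5.2.3: "In the event of any clinical deterioration, a repeat CT scan will be performed immediately". No NIHSS is attached to that scan. Section 6.1 adds: "No additional procedures or assessments will be mandated for study participants".

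**Denominator.** Section 7.1 expresses PH2 and the other grades as a percentage of all patients enrolled.

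**Competing wording.** The Synopsis (Statistical Analyses) gives the primary outcome as PH2 by day 30, and section 7.1 reports the PH2 rate; neither mentions NIHSS. On grading, the Synopsis says "All cases of hemorrhagic transformation seen on day 7 scans will be graded using the ECASS", whereas section 5.2.3 grades hemorrhage on every scan after dabigatran has started.

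**The concern.** The primary event has an imaging half and a clinical half. The plan triggers the imaging half when the event happens, but leaves the clinical half to whatever routine care records. A patient with PH2 who dies before being scored does not meet the definition as written, and because the denominator is everyone enrolled, that patient counts as a success.

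Section 3.1 says safety will be established by showing that hemorrhage is infrequent. A fatal or unscored PH2 that drops out of the numerator moves the answer in exactly that direction. With so few events expected, one such case is a large part of the result. The two statements of the primary outcome make matters worse: the choice between them could be made after the cases are known.

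**Working it through.** **1. The plan's own rate.** Section 2.3 gives 1.7% symptomatic transformation with heparin within a week and a one-third ratio from RE-LY.

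- 1.7% × 1/3 = 0.567%, which reproduces the stated 0.6% after rounding.
- Expected events: 500 × 0.006 = 3.0 (unrounded, 500 × 0.017/3 = 2.8).

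**2. Where a score is assured.** The day 7 assessment has a window of ±2 days, so it falls on days 5 to 9. The outcome window runs to day 30. From day 10 on, no NIHSS is assured by the plan.

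**3. Three illustrative patients (constructed, not taken from the documents).**

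| Patient | Result under the literal definition | What it depends on |
|---|---|---|
| PH2 on day 15, death on day 16, no score after the bleed | Not an event | Only on the absence of a death rule |
| NIHSS 1 at baseline, 8 at PH2 on day 14, 4 at day 30 | 4 − 1 = 3, below 4 | The score of 8 going unrecorded |
| NIHSS 3 at baseline, 0 at first dose, 6 at PH2 | 6 − 3 = 3 from baseline; 6 − 0 = 6 from first dose | Which score is the reference, which is undefined |

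The first patient shows the defect without further assumptions about scoring. The other two show why an event-time score and a stated reference are needed. Appendix 4 has rows only for symptomatic and asymptomatic transformation, so the first patient would have to be placed under asymptomatic or left out.

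**4. Effect of each misclassified case.** One case is 1/500 = 0.2 percentage points. Exact (Clopper-Pearson) 95% intervals:

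| Events counted | Rate | 95% CI |
|---|---|---|
| 3 | 0.6% | 0.12% to 1.74% |
| 2 | 0.4% | 0.05% to 1.44% |
| 1 | 0.2% | 0.01% to 1.11% |
| 0 | 0% | 0 to 0.735% |

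**5. Range over an assumed capture share.** Let *s* be the share of true events that meet the NIHSS condition. The documents give no value, so *s* is varied from 1 to 1/3. Observed rate = true rate × *s*, with a binomial count in 500.

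| *s* | True 0.6%: expected observed rate | True 0.6%: P(0 events) | True 1.7%: P(3 or fewer events) |
|---|---|---|---|
| 1 | 0.6% | 4.9% | 2.9% |
| 2/3 | 0.4% | 13.5% | 18.2% |
| 1/2 | 0.3% | 22.3% | 38.5% |
| 1/3 | 0.2% | 36.8% | 68.5% |

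The last column is the chance of reporting 0.6% or less when the true rate equals the protocol's heparin figure. It rises steeply as capture falls.

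**The case against.** The strongest reply is that these events will not be overlooked. Death is an SAE (5.2.1) and is forwarded within a day or so (5.2.2). Intracranial hemorrhages are centrally adjudicated from clinical records, and every patient has a day 30 form on status and outcome events (6.1). All parenchymal hemorrhages go to the DSMB (Synopsis). The PH2 wording in the Synopsis (Statistical Analyses) and section 7.1 would put a graded PH2 into a reported rate whatever the NIHSS. The study is descriptive and hypothesis-generating (7.2), so no test turns on one case, and the intervals above overlap heavily.

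Most of this stands as a limit on the harm. It does not close the gap, because seeing an event is not classifying it. Nothing authorizes adjudicators to derive a score from the chart or to count death, and the day 30 form does not name NIHSS. The PH2-only wording conflicts with 5.1.2 and does not repair it. A descriptive study is judged on its rate, so the rate's definition matters.

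Several stronger readings are tempting but unsupported:

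- *No NIHSS is taken at deterioration.* The plan specifies none. Recruitment is from Emergency Departments and stroke units (3.3.1) and stroke neurologists prescribe (6.2.2), so a score may well be recorded and reach the adjudicators.
- *Patients treated at other hospitals are lost.* No process for outside hospitals is described, but 5.2.3 collects any brain imaging done within 30 days of enrolment. Loss is conjecture.
- *Fatal cases go unseen.* The reporting routes above say otherwise.
- *A PH2 on a day 15 scan receives no grade.* That follows only if one Synopsis sentence overrides 5.2.3. It is an inconsistency to reconcile.
- *Baseline scoring hides a known number of points.* The reference score and the timing of baseline relative to first dose are both undefined, so no loss is demonstrated.

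**Conclusion.** The concern holds in this form. The primary definition depends on an NIHSS that the plan does not specify at the event, and there is no rule for death, a missing score or the reference score. Read literally, a fatal or unscored PH2 is a non-event in the all-enrolled denominator, which biases the rate downward. Two further inconsistencies should be settled with it: PH2 with or without the NIHSS condition as the primary outcome, and grading of day 7 scans versus all post-dabigatran scans.

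The size is 0.2 percentage points per misclassified case against an expected 0.6%, or about 3 events. How many cases would be lost is unknown; the capture shares used above are assumptions. The conclusion also takes the definition literally: adjudicators might count a fatal PH2 in practice, but the plan does not say that they may. This should be fixed. It does not show that the registry will miss its events.

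**What to change.** 1. **Section 5.1.2 (Primary Outcome).** State that death with PH2 meets the clinical criterion, and that worsening is measured from the last NIHSS recorded before the hemorrhage.
2. **Section 6.1.** With each CT done for deterioration, record the NIHSS obtained in care or, if there is none, one derived from the chart by the site or the adjudicator, and mark which it is.
3. **Primary definition.** Reconcile the Synopsis (Study Endpoints) and 5.1.2 with the Synopsis (Statistical Analyses) and 7.1. Report all PH2 regardless of NIHSS as a sensitivity analysis; this bounds the effect of unscored cases.
4. **Grading.** Align the Synopsis sentence with 5.2.3.

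The cost is protocol wording, a few CRF fields, some chart-derived scores and possibly a slightly higher reported rate. No visit or scan is added. A new mandatory NIHSS at first dose is not proposed, since it would conflict with section 6.1. The rules should be fixed before outcomes are adjudicated, so that they cannot be shaped by the cases.
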